#### 4.2.3 Submitting Regulatory Documents

Submit required forms and documents to the CTSU Regulatory Office using the Regulatory Submission Portal on the CTSU website.

To access the Regulatory Submission Portal log in to the CTSU members' website, go to the Regulatory section and select Regulatory Submission.

Institutions with patients waiting that are unable to use the Regulatory Submission Portal should alert the CTSU Regulatory Office immediately at [name] in order to receive further instruction and support.

#### 4.2.4 Credentialing

See [Section 15.0](#) for credentialing requirements.

### 4.3 Patient Registration Requirements

**Informed consent:** the patient must be aware of the neoplastic nature of his/her disease and willingly consent after being informed of the procedure to be followed, the experimental nature of the therapy, alternatives, potential benefits, side-effects, risks, and discomforts. Current human protection committee approval of this protocol and a consent form is required prior to patient consent and registration.

Patients with impaired decision making capacity may be enrolled on this study, where institutional policy and IRB of record allow.

### 4.4 Patient Registration/Randomization Procedures

The Oncology Patient Enrollment Network (OPEN) is a web-based registration system available on a 24/7 basis. OPEN is integrated with CTSU regulatory and roster data and with the LPOs registration/randomization systems or the Theradex Interactive Web Response System (IWRS) for retrieval of patient registration/randomization assignment. OPEN will populate the patient enrollment data in NCI's clinical data management system, Medidata Rave.

Requirements for OPEN access:

- A valid CTEP-IAM account;
- To perform enrollments or request slot reservations: Must be on an LPO roster, ETCTN corresponding roster, or participating organization roster with the role of Registrar. Registrars must hold a minimum of an Associate Plus (AP) registration type;
- If a Delegation of Tasks Log (DTL) is required for the study, the registrars must hold the OPEN Registrar task on the DTL for the site; and
- Have an approved site registration for the protocol prior to patient enrollment.

To assign an Investigator (IVR) or Non-Physician Investigator (NPiVR) as the treating, crediting, consenting, drug shipment (IVR only), or receiving investigator for a patient transfer in OPEN, the IVR or NPiVR must list the IRB number used on the site's IRB approval on their Form FDA 1572 in RCR. If a DTL is required for the study, the IVR or NPiVR must be assigned the appropriate OPEN-related tasks on the DTL.

Prior to accessing OPEN, site staff should verify the following:

- Patient has met all eligibility criteria within the protocol stated timeframes; and
- All patients have signed an appropriate consent form and HIPAA authorization form (if applicable).

Note: The OPEN system will provide the site with a printable confirmation of registration and treatment information. You may print this confirmation for your records.

Access OPEN at <https://open.ctsu.org> or from the OPEN link on the CTSU members' website. Further instructional information is in the OPEN section of the CTSU website at <https://www.ctsu.org> or <https://open.ctsu.org>. For any additional questions, contact the CTSU Help Desk at [name] or [[contact]](mailto:[contact]).

### 4.5 Stratification Factors and Treatment Assignments

Number of metastases (2-4 vs. >4)

Age <70 vs. ≥ 70 years old

ECOG 0-1 vs 2

## 5.0 STUDY CALENDAR

The pre-study testing intervals are guidelines only. Laboratory and clinical parameters during treatment are to be followed using individual institutional guidelines and the best clinical judgment of the responsible physician. It is expected that patients on this study will be cared for by physicians experienced in the treatment and supportive care of patients on this trial.

- To be completed  $\leq 28$  DAYS before registration: All laboratory studies, history and physical.
- To be completed  $\leq 28$  DAYS before registration: Any X-ray, scan of any type or ultrasound which is utilized for tumor measurement per protocol.
- To be completed  $\leq 28$  DAYS before registration: Any baseline exams used for screening, or any X-ray, scan of any type or ultrasound of uninvolved organs which is not utilized for tumor measurement.

	Prior to Registration*	Arm 2 only: Radiation***	Arms 1&2 (MK3475): Day 1 of each cycle	Post treatment follow-up**
Tests & Observations				
History and physical, weight, PS	X	X	X	X
Height	X			
Adverse Event Assessment		X	X	X
Registration Fatigue/Uniscale Assessment	X(1)			
Laboratory Studies				
Complete Blood Count, Differential, Platelets	X		X	X
Serum Creatinine, Albumin, glucose	X		X	X
AST, ALT, Alk. Phos., Bili	X		X	X
TSH (with reflexive TFTs if abnormal)	X		X	X
Serum or Urine HCG	X(2)			
Staging				
Brain Imaging (MRI or CT with contrast)†	X			
Tumor Measurement	X		A	X
CT/MRI chest/abd/pelvis #	X(3)		A	X
Correlative studies: For patients who consent to participate				
Blood samples	Collected at baseline, after RT (prior to pembrolizumab (MK-3475)(Arm 2 patients only), day 1 of cycle 3, and at the time of first restaging imaging (i.e. 3 months after cycle 1), see Section 6.2.			
Tissue	Collected at baseline prior to any treatment			

\* Labs completed prior to registration may be used for day 1 of cycle 1 tests if obtained  $\leq 7$  days prior to treatment. For subsequent cycles, labs, scans, tests and observations may be obtained  $\leq 72$  hours prior to day of treatment.

- \*\* Physical examination, adverse event assessments, labs and scans are required  $\leq 12$  weeks after the end of treatment; thereafter, every 6 months until disease progression for a maximum of 5 years following registration or more frequently as clinically indicated. See also [Section 12.0](#). At time of progression, withdrawal or removal, only survival information should be collected every 6 months for 5 years after registration.
- \*\*\* Radiation therapy will be administered to 1 cancer deposit concurrent with the first dose or started within the first cycle of pembrolizumab (MK-3475) administration. Eligibility must have been documented prior to administration of radiation.
- † Only required if there is evidence or suspected brain mets
- # All sites of known disease as clinically indicated.
- 1 To be completed after registration and prior to treatment (See Appendix I). This questionnaire is included on all Alliance trials in order to further study the relationship between these assessments and overall survival in a meta-analysis setting.
- 2 For women of childbearing potential (see [Section 3.2](#)). Must be done  $\leq 7$  days prior to registration.
- 3 Baseline scans can include either: 1) a CT, spiral CT, or MRI or 2) an FDG-PET scan and diagnostic CT performed with both IV and oral contrast, and the CT acquired with 5 mm or less slice thickness. Supporting documentation is to be submitted, per [Section 6.1](#). Response assessment should include assessment of all sites of disease and use the same imaging method as was used at baseline.
- A After Cycle 3 (prior to cycle 4) then every 9 weeks, (prior to the start of cycles 4, 7, 10, 13, 15, etc.).

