### **7.0 TREATMENT PLAN/INTERVENTION**

Protocol treatment is to begin  $\leq 21$  days of registration.

For questions regarding treatment, please see the study contacts page.

It is acceptable for individual pembrolizumab (MK-3475) to be delivered  $\leq$  a 72-hour (business day) window before and after the protocol-defined date for Day 1 of a new cycle. For example, if the treatment due date is a Friday, the window for treatment includes the preceding Tuesday through the following Monday. In addition, patients are permitted to have a new cycle of pembrolizumab (MK-3475) delayed up to 7 days for major life events (e.g., serious illness in a family member, major holiday, vacation that cannot be rescheduled) without this being considered a protocol violation. Documentation to justify this delay should be provided.

Pembrolizumab (MK-3475) is administered on an outpatient basis. Infusion timing should be as close to 30 minutes as possible; however, a window of -5 minutes and +10 minutes is permitted (*i.e.*, infusion time is 25-40 minutes). Please refer to Section 10.2 for pembrolizumab (MK-3475) compatible infusion set materials, including in-line filter.

Protocol therapy will include pembrolizumab (MK-3475) in both arms (Arms 1 & 2) and radiation (SBRT) in one arm (Arm 2). Radiation will be administered concurrent with the first dose or started

within the first cycle of pembrolizumab (MK-3475). The radiated lesion will be identified prior to randomization and that this lesion will be excluded from the primary endpoint (PFS) calculation. pembrolizumab (MK-3475) treatment will be administered once every 21 days (1 cycle). Treatment will continue until disease progression or unacceptable adverse event for a maximum period of two years.

Agent	Dose	Route	Day	ReRx
pembrolizumab (MK-3475)	200 mg	IV	Day 1	every 3 weeks

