### 7.1.8 Submission of Digital Radiation Therapy Data

Submission of treatment plans in digital format as DICOM RT is required. Digital data must include CT scans, structures, plan, and dose files. This study uses TRIAD for RT data submission. Use of TRIAD requires several preliminary steps. See [Section 6.3](#) for details. Additional information is available at:

<http://triadhelp.acr.org/ClinicalTrials/NCISponsoredTrials.aspx>

Any items on the list below that are not part of the digital submission may be included with the transmission of the digital RT data.

One week prior to the start of radiotherapy, the following data shall be submitted for pre-treatment review for all cases:

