### 11.1 Schedule of Evaluations

For the purposes of this study, patients should be reevaluated every 9 weeks.

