#### 13.2 Statistical Design and Analysis for the Primary Endpoint

##### 13.2.1 Primary Endpoint:

We are comparing the Progression Free Survival (PFS) in non-radiated lesion(s) of patients receiving either (a) SBRT + pembrolizumab (MK-3475) compared to (b) pembrolizumab (MK-3475) alone in patients with advanced Merkel cell carcinoma. For each patient, during screening, one lesion will be identified as the one to be potentially radiated (if randomized to the arm with SBRT). Then up to 5 additional lesions will be identified that are followed for PFS. For patients in both arms, the lesion identified to be radiated (pre-randomization) will be followed separately (i.e. it will not be a target lesion). If this lesion changes in a way that leads to a change in the patient's treatment (e.g. adding a non-protocol treatment or removal of the patient from the study), then the patient's PFS data would be considered censored at the time of the change in their treatment.

A patient is considered an event for this endpoint at the time of first evidence of disease progression or death (without evidence of progression) and their PFS time is defined as the time from randomization to either disease progression or death (without progression). For patients that are not considered an event for this endpoint, the PFS time will be censored at their last evaluation for progression. All randomized patients meeting the eligibility criteria who received any quantity of their randomized care and did not have a major treatment violation will be part of the analysis group for the primary endpoint.

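### Scans follow pembrolizumab cycles while PFS runs from randomization, so a later cycle 1 in the SBRT arm, if it occurs, would bias the hazard ratio toward SBRT, and nothing in the analysis plan guards against it.

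*Combined protocol and SAP*

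**What the plan says.** **Clock for the endpoint.** Section 13.2.1 starts PFS at randomization: "their PFS time is defined as the time from randomization to either disease progression or death (without progression".

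**Clock for the scans.** Footnote A of the Section 5.0 calendar puts the first on-treatment scan before cycle 4 and the rest "then every 9 weeks, (prior to the start of cycles 4, 7, 10, 13, 15, etc". Section 11.1 says only "patients should be reevaluated every 9 weeks" and gives no start date for the count.

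**Start of treatment.** Section 7.0 sets one limit for both arms: treatment begins within 21 days of registration.

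**Steps in Arm 2 only.** Radiotherapy needs simulation and motion assessment (Tables 1.2 and 1.3), planning (Section 7.1.4) and central review of each case (Section 15.1.2). Section 7.1.8 adds: "One week prior to the start of radiotherapy, the following data shall be submitted for pre-treatment review for all cases".

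**Order of SBRT and first dose.** Section 5.0 states: "Radiation therapy will be administered to 1 cancer deposit concurrent with the first dose or started within the first cycle of pembrolizumab (MK-3475) administration". The Schema and Section 7.0 agree, so pembrolizumab may start first. Two places point the other way. The correlative row of the calendar puts an Arm 2 blood draw after radiotherapy and before pembrolizumab, and Section 8.0 speaks of pembrolizumab exposure that follows radiation.

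**Analysis.** Section 13 has no randomization-based scan window, no interval-censored method and no sensitivity analysis for assessment timing.

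**The concern.** Progression is dated at the scan that finds it. If Arm 2 scans fall a few days after the matching Arm 1 scans on the randomization clock, each batch of Arm 1 progressions is counted while Arm 2 patients who have already progressed, but have not yet been scanned, still sit in the risk set. The log-rank comparison then credits SBRT with a delay that belongs to the calendar.

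The margin is narrow. The trial is judged promising or not by a fixed hazard-ratio cut-off of 0.837 at one-sided alpha 0.20 (Section 13.2.2), so a spurious shift of a few hundredths changes the error rate visibly.

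Arm 2 has preparatory steps that Arm 1 lacks, and a site that gives SBRT together with the first dose has to wait for the plan. A lag is therefore plausible.

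**Working it through.** **1. The plan's own design reproduces.** Take log HR as normal with variance 4/events, 38 events at the interim look and 75 at the final, so the correlation between looks is √(38/75) = 0.712.

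- Final cut-off: z = −ln(0.837) × √75/2 = 0.1779 × 4.330 = 0.770. Its tail probability is 0.221 without the interim look.
- Interim cut-off: z = −ln(1.013) × √38/2 = −0.040.
- Joint probability of passing both: 0.199 at HR 1 and 0.802 at HR 0.667. The plan states 0.20 and 80%.

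**2. Hand check of the mechanism.** Assume no treatment effect, 48 patients per arm, median 9 months (9 × 30.44 = 273.9 days), 63-day scan intervals, all events found by scan, and Arm 2 scans always slightly later than the matching Arm 1 scans.

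- Probability of progression per interval: 1 − exp(−0.6931 × 63/273.9) = 0.147, or 7.07 events per arm in the first round.
- Arm 1 batch: Arm 2 observed 0, expected 7.07 × 48/96 = 3.54. O − E = −3.54.
- Arm 2 batch: 40.93 left at risk in Arm 1, so Arm 2's share is 48/88.93 = 0.540. Expected 3.82, observed 7.07. O − E = +3.25.
- Sum ≈ −0.28. Variance: 7.07 × 0.25 × 88.93/95 + 7.07 × 0.540 × 0.460 × 81.86/87.93 ≈ 1.65 + 1.64 = 3.29.
- exp(−0.28/3.29) ≈ 0.92.

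Later rounds repeat this on smaller risk sets. The bias comes from the separation of the scan batches, not from the number of days as such.

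**3. Simulation with rigid scans.** Inputs from the plan: 96 patients, 3 per month, median 9 months in both arms, 9-week scans, looks at 38 and 75 events with cut-offs 1.013 and 0.837. Assumptions: 10% of events are exactly dated deaths, cycle 1 is otherwise spread over 0–7 days, and Arm 2 is shifted by the lag shown. 6,000 trials per row; Monte Carlo standard error about 0.005 (√(0.2 × 0.8/6000)).

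| Arm 2 lag (days) | Median HR, cycle anchor | False positive, cycle anchor | False positive, randomization anchor |
|---|---|---|---|
| 0 | 1.00 | 0.21 | 0.21 |
| 3 | 0.95 | 0.27 | 0.20 |
| 7 | 0.93 | 0.31 | 0.21 |
| 14 | 0.95 | 0.28 | 0.20 |
| 21 | 0.97 | 0.25 | 0.21 |

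At a 7-day lag, varying the exactly dated deaths from 0 to 30% and the cycle 1 spread from 0 to 21 days gives HR 0.91–0.96 and false positive 0.26–0.33. The effect does not grow steadily with the lag. A larger shift also lengthens the first Arm 2 scan interval, which then captures more events.

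**4. Simulation with scan scatter.** Same rules, adding the 72-hour dosing and scan windows of Sections 7.0 and 5.0 and, as assumptions, 7-day delays in 5% of cycles and 10% exactly dated events. 3,000 trials per row; standard error about 0.007.

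| Cycle 1 start, Arm 1 vs Arm 2 (days) | HR | False positive |
|---|---|---|
| 0–21 vs 0–21 | 1.00 | 0.21 |
| 0–14 vs 3–17 | 0.98 | 0.22 |
| 0–21 vs 3–21 | 0.98 | 0.21 |
| 0–21 vs 7–21 | 0.98 | 0.24 |
| 0–14 vs 7–21 (mean lag 7) | 0.97 | 0.24 |

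**5. The cycle list.** Nine weeks is three 21-day cycles, so 16 follows 13 (13 + 3). The listed 15 is a 6-week gap. This affects both arms alike and gives no directional bias.

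**The case against.** The strongest reply is that the causal link is assumed. No passage says that cycle 1 is later in Arm 2. SBRT may start after the first dose within cycle 1, the one-week submission lead precedes radiotherapy rather than pembrolizumab, the lesion is chosen before randomization, and both arms share the 21-day limit. All of this stands. A reader might infer that the schedule builds in an advantage for SBRT; the documents do not support that.

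The calendar's blood draw is weak evidence, because it belongs to optional biobanking and the specimen table in Section 6.3.1 says only that it follows radiotherapy. That also stands. What remains is a conflict on the order of SBRT and first dose, which has to be reconciled.

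A reader might also take a much larger inflation as the expected one. With non-overlapping start windows (0.5–1.5 vs 1.5–2.5 weeks), every event dated by scan and no interim look, a one-week lag gives HR 0.92 and a 0.34 chance of falling below 0.837, against 0.23 with equal delays. That is near the worst case. Overlapping starts and ordinary scatter bring the excess down to about 0.03 or less over the equal-start rate.

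Holds for toxicity also move scans, but they occur in both arms and no passage gives a difference between them.

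Finally, accrual is closed, so new calendar wording cannot move scans already done. This is correct, and it shifts the weight of the remedy to the analysis.

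**Conclusion.** The mismatch between the scan clock and the PFS clock is in the text, and Section 13 does not guard against it. Whether it biases this trial depends on one fact that the documents do not give: the difference between arms in time from randomization to cycle 1.

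- No difference: no bias (HR 1.00, false positive 0.20–0.21).
- Assumed mean lag of about one week in Arm 2, no true effect: HR about 0.97 and false positive about 0.24 with realistic scatter; about 0.93 and 0.31 with rigid scans.
- The bias favoured SBRT in the rigid-scan runs at every lag tried from 3 to 21 days. With scatter, the smallest lags cannot be told from equal starts within simulation error.

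These sizes rest on exponential PFS with a 9-month median, the assumed lag and spread, and the assumed share of exactly dated deaths. The point should be fixed, conditional on an arm difference in cycle 1 timing; it is not an established bias.

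**What to change.** **For data already collected (the main step).**
- Tabulate by arm the time from randomization to cycle 1 and to each scan. If the arms match, the concern closes.
- Before the primary analysis, prespecify in Section 13.2.3 a sensitivity analysis of primary PFS that either dates progression by nominal scan number (first, second, third) in a grouped log-rank test or uses an interval-censored log-rank test.

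**For the text.**
- In footnote A and Section 11.1, schedule assessments in both arms at weeks 9, 18, 27 and so on from randomization, with a window such as ±7 days, whatever the cycle delays or holds. For patients still on treatment, record the date of the change, since the two schedules would then be mixed.
- Remove the cycle list that runs 13, 15.
- Reconcile the calendar's correlative row and Section 8.0 with the Schema, Section 5.0 and Section 7.0 on the order of SBRT and first dose.

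**Cost.** One table, one extra analysis and a wording change. The 9-week frequency is unchanged, but some scans will no longer fall on dosing visits.

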## 6.0 DATA AND SPECIMEN SUBMISSION

### 6.1 Data Collection and Submission

#### 6.1.1 Data submission schedule

A Data Submission Schedule (DSS) is available on the Alliance study webpage, within the Case Report Forms section. The Data Submission Schedule is also available on the CTSU site within the study-specific Case Report Forms folder.

#### 6.1.2 Medidata Rave

Medidata Rave is a clinical data management system being used for data collection for this trial/study. Access to the trial in Rave is controlled through the CTEP-IAM system and role assignments.

Requirements to access Rave via iMedidata:

- A valid CTEP-IAM account; and
- Assigned a Rave role on the LPO or PO roster at the enrolling site of: Rave CRA, Rave Read Only, Rave CRA (LabAdmin), Rave SLA, or Rave Investigator.

Rave role requirements:

- Rave CRA or Rave CRA (Lab Admin) role must have a minimum of an Associate Plus (AP) registration type;
- Rave Investigator role must be registered as an Non-Physician Investigator (NPIVR) or Investigator (IVR); and
- Rave Read Only role must have at a minimum an Associates (A) registration type.

Refer to <https://ctep.cancer.gov/investigatorResources/default.htm> for registration types and documentation required.

This study has a Delegation of Tasks Log (DTL). Therefore, those requiring write access to Rave must also be assigned the appropriate Rave tasks on the DTL.

Upon initial site registration approval for the study in Regulatory Support System (RSS), all persons with Rave roles assigned on the appropriate roster will be sent a study invitation e-mail from iMedidata. To accept the invitation, site staff must log in to the Select Login (<https://login.imedidata.com/selectlogin>) using their CTEP-IAM username and password and click on the accept link in the upper right-corner of the iMedidata page. Site staff will not be able to access the study in Rave until all required Medidata and study specific trainings are completed. Trainings will be in the form of electronic learnings (eLearnings) and can be accessed by clicking on the link in the upper right pane of the iMedidata screen. If an eLearning is required and has not yet been taken, the link to the eLearning will appear under the study name in iMedidata instead of the Rave EDC link; once the successful completion of the eLearning has been recorded, access to the study in Rave will be granted, and a Rave EDC link will display under the study name.

Site staff that have not previously activated their iMedidata/Rave account at the time of initial site registration approval for the study in RSS will receive a separate invitation from iMedidata to activate their account. Account activation instructions are located on the CTSU website in the Data Management section under the Rave resource materials (Medidata Account Activation and Study Invitation Acceptance). Additional information on iMedidata/Rave is available on the CTSU members' website in the Data Management

> Rave section at [www.ctsu.org/RAVE/](http://www.ctsu.org/RAVE/) or by contacting the CTSU Help Desk at [name] or by e-mail at [[contact]](mailto:[contact]).

ePRO:

The data from the patients' responses are submitted directly from the device into the Rave database. There are no documents to audit. The electronic responses are the source documentation.

